3.0054	All Treated	See programming notes	Shift in Lens Exam Results from Baseline to Worst Post-Baseline	
Report for: Part 1, Part 2, and combined Part 1 and Part 2; Summarize by dose level (refer to Section 5.1 for ordering of dose level and omit 1.92 mg/kg if data is not available; Total; Refer to mid205678 (primary_01) Table 3.1000 and Table 3.1020 for guidance. Categories are "No" and "Yes"; Include the following lens exams: Lens Clear, Pseudophakia, Nuclear Sclerosis, Cortical Cataract, Posterior Subcapsular Cataract
 
Add the following footnote:
 
Note: Baseline percentage is based on N. Percentage for worst post-Baseline value is based on Baseline n.
	P-SAC [3], F-SAC [4]

Safety: Tables					
No.	Population	IDSL / Example Shell	Title	Programming Notes	Deliverable [Priority]
3.0055	All Treated	See programming notes	Summary of Best Corrected Visual Acuity Test (BCVA) Scores (logMAR score)	Report for: Part 1, Part 2, and combined Part 1 and Part 2; Summarize by: dose level (Refer to Section 5.1 for ordering of dose level and omit 1.92 mg/kg if data is not available) Total.; Refer to mid205678 (primary_01) Table 3.0730 for guidance.	P-SAC [3], F-SAC [4]
3.0056	Safety	See programming notes	Number (%) of Subjects with a Decline in Best Corrected Visual Acuity (BCVA) to LP or NLP due Anytime Post-Baseline	Report for: Part 1, Part 2, and combined Part 1 and Part 2; Summarize by: dose level (Refer to Section 5.1 for ordering of dose level and omit 1.92 mg/kg if data is not available) Total.; Refer to mid205678 (primary_01) Table 3.0740 for guidance.	P-SAC [3], F-SAC [4]

Safety: Tables					
No.	Population	IDSL / Example Shell	Title	Programming Notes	Deliverable [Priority]
3.0057	Safety	Mock-up SAFE_T1	Summary of Worst Post-Baseline Best Corrected Visual Acuity (BCVA) Change in Snellen Results	
Report for: Part 1, Part 2, and combined Part 1 and Part 2; Summarize by: dose level (Refer to Section 5.1 for ordering of dose level and omit 1.92 mg/kg if data is not available) Total.; Percentages should be computed out of big N. Add the following footnotes:
 
[1]: Number of lines change from baseline is defined as the following: Improved BCVA equates to a negative change in logMAR from baseline BCVA. <=2 Lines decline in Visual Acuity equates to logMAR change from baseline <=0.37 (or CCI [REDACTED] decline as defined by GSK Scale). >=3 Lines decline in Visual Acuity equates to logMAR change from baseline >=0.38 (or CCI [REDACTED] decline as defined by GSK Scale).
 
Note: 'n' denotes subjects who have any post-baseline Best Corrected Visual acuity (BCVA) score.
	P-SAC [3], F-SAC [4]

Safety: Tables					
No.	Population	IDSL / Example Shell	Title	Programming Notes	Deliverable [Priority]
Deaths					
3.0058	All Treated	DD1	Summary of Deaths	Report for: Part 1, Part 2, and combined Part 1 and Part 2; Summarize by: dose level (Refer to Section 5.1 for ordering of dose level and omit 1.92 mg/kg if data is not available) Total. Use ranges '<= 30 days' and '> 30 days' for "time to death from last dose"	P-SAC [3], F-SAC [4]
Laboratory: Chemistry					
3.0059	All Treated	LB1	Summary of Chemistry Changes from Baseline	Report for: Part 1, Part 2, and combined Part 1 and Part 2; ; Summarize by: dose level (Refer to Section 5.1 for ordering of dose level and omit 1.92 mg/kg if data is not available) Total. Include baseline values; .	P-SAC [3], F-SAC [4]
3.0060	All Treated	LB16	Summary of Worst Case Chemistry Results by Maximum Grade Increase Post-Baseline Relative to Baseline	Report for: Part 1, Part 2, and combined Part 1 and Part 2; ; Summarize by: dose level (Refer to Section 5.1 for ordering of dose level and omit 1.92 mg/kg if data is not available) Total.; For categories, use only "Any Grade Increase", "Increase to Grade 3" and "Increase to Grade 4"	P-SAC [3], F-SAC [4]

Safety: Tables					
No.	Population	IDSL / Example Shell	Title	Programming Notes	Deliverable [Priority]
3.0061	All Treated	LB15	Summary of Worst Case Chemistry Results Relative to Normal Range Post-Baseline Relative to Baseline	Report for: Part 1, Part 2, and combined Part 1 and Part 2; ; Summarize by: dose level (Refer to Section 5.1 for ordering of dose level and omit 1.92 mg/kg if data is not available) Total.; For categories, use "Decrease to Low", "Change to Normal or No Change", and "Increase to High"	P-SAC [3], F-SAC [4]
Laboratory: Hematology					
3.0062	All Treated	LB1	Summary of Hematology Changes from Baseline	Report for: Part 1, Part 2, and combined Part 1 and Part 2; ; Summarize by: dose level (Refer to Section 5.1 for ordering of dose level and omit 1.92 mg/kg if data is not available) Total. Include baseline values;	P-SAC [3], F-SAC [4]
3.0063	All Treated	LB16	Summary of Worst Case Hematology Results by Maximum Grade Increase Post-Baseline Relative to Baseline	Report for: Part 1, Part 2, and combined Part 1 and Part 2; ; Summarize by: dose level (Refer to Section 5.1 for ordering of dose level and omit 1.92 mg/kg if data is not available) Total.; For categories, use only "Any Grade Increase", "Increase to Grade 3" and "Increase to Grade 4"	P-SAC [3], F-SAC [4]
3.0064	All Treated	LB15	Summary of Worst Case Hematology Results Relative to Normal Range Post-Baseline Relative to Baseline	Report for: Part 1, Part 2, and combined Part 1 and Part 2; ; Summarize by: dose level (Refer to Section 5.1 for ordering of dose level and omit 1.92 mg/kg if data is not available) Total.; For categories, use "Decrease to Low", "Change to Normal or No Change", and "Increase to High"	P-SAC [3], F-SAC [4]

Safety: Tables					
No.	Population	IDSL / Example Shell	Title	Programming Notes	Deliverable [Priority]
Laboratory: Urinalysis					
3.0065	All Treated	LB1	Summary of Urine Concentration Changes from Baseline	Report for: Part 1, Part 2, and combined Part 1 and Part 2; ; Summarize by: dose level (Refer to Section 5.1 for ordering of dose level and omit 1.92 mg/kg if data is not available) Total. Include baseline values	P-SAC [3], F-SAC [4]
3.0066	All Treated	OUR1B	Summary of Urinalysis Results (Discrete or Character Values) by Visit	Report for: Part 1, Part 2, and combined Part 1 and Part 2; Summarize by: dose level (Refer to Section 5.1 for ordering of dose level and omit 1.92 mg/kg if data is not available) Total. For protein, occult blood, ketones, and glucose dipstick tests, remove "increase" columns and "Worst-case post baseline" row for dose levels and add "presence" and "absence" columns.	P-SAC [3], F-SAC [4]
3.0067	All treated	UR1	Summary of Worst Case Urinalysis Results Post Baseline Relative to Baseline	Report for: Part 1, Part 2, and combined Part 1 and Part 2; Summarize by: dose level (Refer to Section 5.1 for ordering of dose level and omit 1.92 mg/kg if data is not available) Total. Include only 'n', 'No Change/Decreased' and 'Any Increase' categories	F-SAC [4]

Safety: Tables					
No.	Population	IDSL / Example Shell	Title	Programming Notes	Deliverable [Priority]
Laboratory: Hepatobiliary (Liver)					
3.0068	All Treated	LIVER1	Summary of Liver Monitoring/Stopping Event Reporting	Report for: Part 1, Part 2, and combined Part 1 and Part 2; Summarize by: dose level (Refer to Section 5.1 for ordering of dose level and omit 1.92 mg/kg if data is not available) Total. If less than 5 participants, produce listing instead.	P-SAC [3], F-SAC [4]
3.0069	All Treated	LIVER10	Summary of Hepatobiliary Laboratory Abnormalities	Report for: Part 1, Part 2, and combined Part 1 and Part 2; Summarize by: dose level (Refer to Section 5.1 for ordering of dose level and omit 1.92 mg/kg if data is not available) Total.	P-SAC [3], F-SAC [4]
3.0070	All Treated	LIVER11	Summary of Liver Restart/Re-Challenges	Report for: Part 1, Part 2, and combined Part 1 and Part 2; Summarize by: dose level (Refer to Section 5.1 for ordering of dose level and omit 1.92 mg/kg if data is not available) Total.	P-SAC [3], F-SAC [4]
ECG					
3.0071	All Treated	EG1	Summary of ECG Findings	Report for: Part 1, Part 2, and combined Part 1 and Part 2; Summarize by: dose level (Refer to Section 5.1 for ordering of dose level and omit 1.92 mg/kg if data is not available) Total.	P-SAC [3], F-SAC [4]

Safety: Tables					
No.	Population	IDSL / Example Shell	Title	Programming Notes	Deliverable [Priority]
3.0072	All Treated	EG10	Summary of Maximum QTc Values Post-Baseline Relative to Baseline by Category	Report for: Part 1, Part 2, and combined Part 1 and Part 2; Summarize by: dose level (Refer to Section 5.1 for ordering of dose level and omit 1.92 mg/kg if data is not available) Total; For categories, use only "Any Grade Increase", "Increase to Grade 2" and "Increase to Grade 3"; Worst case post-baseline only	P-SAC [3], F-SAC [4]
3.0073	All Treated	EG2	Summary of Change from Baseline in ECG Values by Visit	Report for: Part 1, Part 2, and combined Part 1 and Part 2; Summarize by: dose level (Refer to Section 5.1 for ordering of dose level and omit 1.92 mg/kg if data is not available) Total.	P-SAC [3], F-SAC [4]
3.0074	All Treated	EG11	Summary of Maximum Increase in QTc Values Post-Baseline Relative to Baseline by Category	Report for: Part 1, Part 2, and combined Part 1 and Part 2; Summarize by: dose level (Refer to Section 5.1 for ordering of dose level and omit 1.92 mg/kg if data is not available) Total; Worst case post-baseline only.	P-SAC [3], F-SAC [4]

Safety: Tables					
No.	Population	IDSL / Example Shell	Title	Programming Notes	Deliverable [Priority]
Vital Signs					
3.0075	All Treated	VS1	Summary of Change from Baseline in Vital Signs	Report for: Part 1, Part 2, and combined Part 1 and Part 2; Summarize by: dose level (Refer to Section 5.1 for ordering of dose level and omit 1.92 mg/kg if data is not available) Total.	P-SAC [3], F-SAC [4]
3.0076	All Treated	VS6	Summary of Worst Case Vital Signs Results by Maximum Grade Increase Post-Baseline Relative to Baseline	Report for: Part 1, Part 2, and combined Part 1 and Part 2; Summarize by: dose level (Refer to Section 5.1 for ordering of dose level and omit 1.92 mg/kg if data is not available) Total	P-SAC [3], F-SAC [4]
3.0077	All Treated	VS3	Summary of Worst Case Vital Signs Results Relative to Normal Range Post-Baseline Relative to Baseline	Report for: Part 1, Part 2, and combined Part 1 and Part 2; Summarize by: dose level (Refer to Section 5.1 for ordering of dose level and omit 1.92 mg/kg if data is not available), Total;	P-SAC [3], F-SAC [4]
LVEF					
3.0078	All Treated	LVEF1A	Summary of Left Ventricular Ejection Fraction Change from Baseline	Report for: Part 1, Part 2, and combined Part 1 and Part 2; Summarize by: dose level (Refer to Section 5.1 for ordering of dose level and omit 1.92 mg/kg if data is not available), Total; Worst case post-baseline only Footnote: LLN: Normal Range Lower Limit.	P-SAC [3], F-SAC [4]

Safety: Tables					
No.	Population	IDSL / Example Shell	Title	Programming Notes	Deliverable [Priority]
Dose Modifications					
3.0079	All Treated	ODMOD1	Summary of Dose Reductions of GSK2857916	Report for: Part 1, Part 2, and combined Part 1 and Part 2; Summarize by: dose level (Refer to Section 5.1 for ordering of dose level and omit 1.92 mg/kg if data is not available), Total;	P-SAC [3], F-SAC [4]
3.0080	All Evaluable	ODMOD1	Summary of Dose Reductions of GSK2857916	Report for: futility interim analyses for part 2 participants and part 1 participants who initially received the RP2D (Refer to Section 5.1 for ordering of dose level); Include the following footnote: "Note: A subject is evaluable for interim analysis if they meet at least one of these criteria: (More than 66 days in study and had at least three disease assessments) OR had at least one disease assessment on or after day 60 OR had an unconfirmed response of PR/CR or better OR progressed OR died OR discontinued treatment."	IA [1]

Safety: Tables					
No.	Population	IDSL / Example Shell	Title	Programming Notes	Deliverable [Priority]
3.0081	All Treated	ODMOD3	Summary of Dose Delays of GSK2857916	Report for: Part 1 and Part 2, and combined Part 1 and Part 2; Summarize by: dose level (Refer to Section 5.1 for ordering of dose level and omit 1.92 mg/kg if data is not available), Total; Include summary statistics. Include the following footnote: "Note: The protocol allows a window of \pm 3 days for administration of study treatment after Cycle 1 so a dose will only be considered delayed if it is 4 or more days after the scheduled dose date."	P-SAC [3], F-SAC [4]

Safety: Tables					
No.	Population	IDSL / Example Shell	Title	Programming Notes	Deliverable [Priority]
3.0082	All Evaluable	ODMOD3	Summary of Dose Delays of GSK2857916	
Report for: futility interim analyses for part 2 participants and part 1 participants who initially received the RP2D (Refer to Section 5.1 for ordering of dose level); Include summary statistics.
 
Include the following footnote(s): “Note: The protocol allows a window of \pm 3 days for administration of study treatment after Cycle 1 so a dose will only be considered delayed if it is 4 or more days after the scheduled dose date.”
 
“Note: A subject is evaluable for interim analysis if they meet at least one of these criteria: (More than 66 days in study and had at least three disease assessments) OR had at least one disease assessment on or after day 60 OR had an unconfirmed response of PR/CR or better OR progressed OR died OR discontinued treatment.”
	IA [1]

Safety: Tables					
No.	Population	IDSL / Example Shell	Title	Programming Notes	Deliverable [Priority]
3.0083	All Treated	ODMOD3	Summary of Dose Delays of Pembrolizumab	
Report for: Part 1, Part 2, and combined Part 1 and Part 2; Summarize by: dose level (Refer to Section 5.1 for ordering of dose level and omit 1.92 mg/kg if data is not available), Total; Include summary statistics.
 
Include the following footnote: "Note: The protocol allows a window of \pm 3 days for administration of study treatment after Cycle 1 so a dose will only be considered delayed if it is 4 or more days after the scheduled dose date."
	P-SAC [3], F-SAC [4]

Safety: Tables					
No.	Population	IDSL / Example Shell	Title	Programming Notes	Deliverable [Priority]
3.0084	All Evaluable	ODMOD3	Summary of Dose Delays of Pembrolizumab	
Report for: futility interim analyses for part 2 participants and part 1 participants who initially received the RP2D (Refer to Section 5.1 for ordering of dose level);
 
Include summary statistics.
 
Include the following footnote(s): “Note: The protocol allows a window of \pm 3 days for administration of study treatment after Cycle 1 so a dose will only be considered delayed if it is 4 or more days after the scheduled dose date.”
 
“Note: A subject is evaluable for interim analysis if they meet at least one of these criteria: (More than 66 days in study and had at least three disease assessments) OR had at least one disease assessment on or after day 60 OR had an unconfirmed response of PR/CR or better OR progressed OR died OR discontinued treatment.”
	IA [1]
3.0085	All Treated	ODMOD16	Summary of Infusion Interruptions of GSK2857916	Report for: Part 1, Part 2, and combined Part 1 and Part 2; Summarize by: dose level (Refer to Section 5.1 for ordering of dose level and omit 1.92 mg/kg if data is not available), Total;	P-SAC [3], F-SAC [4]

Safety: Tables					
No.	Population	IDSL / Example Shell	Title	Programming Notes	Deliverable [Priority]
3.0086	All Evaluable	ODMOD16	Summary of Infusion Interruptions of GSK2857916	Report for: futility interim analyses for part 2 participants and part 1 participants who initially received the RP2D (Refer to Section 5.1 for ordering of dose level).Include the following footnote: "Note: A subject is evaluable for interim analysis if they meet at least one of these criteria: (More than 66 days in study and had at least three disease assessments) OR had at least one disease assessment on or after day 60 OR had an unconfirmed response of PR/CR or better OR progressed OR died OR discontinued treatment."	IA [1]
3.0087	All Treated	ODMOD16	Summary of Infusion Interruptions of Pembrolizumab	Report for: Part 1, Part 2, and combined Part 1 and Part 2; Summarize by: dose level (Refer to Section 5.1 for ordering of dose level and omit 1.92 mg/kg if data is not available), Total;	P-SAC [3], F-SAC [4]

Safety: Tables					
No.	Population	IDSL / Example Shell	Title	Programming Notes	Deliverable [Priority]
3.0088	All Evaluable	ODMOD16	Summary of Infusion Interruptions of Pembrolizumab	Report for: futility interim analyses for part 2 participants and part 1 participants who initially received the RP2D (Refer to Section 5.1 for ordering of dose level).Include the following additional footnote for IA only: "Note: A subject is evaluable for interim analysis if they meet at least one of these criteria: (More than 66 days in study and had at least three disease assessments) OR had at least one disease assessment on or after day 60 OR had an unconfirmed response of PR/CR or better OR progressed OR died OR discontinued treatment.	IA [1]

Safety: Tables					
No.	Population	IDSL / Example Shell	Title	Programming Notes	Deliverable [Priority]
Dose Limiting Toxicity (DLT)					
3.0089	DLT Evaluable	AE19	Summary of Dose-Limiting Toxicities during the Determinative Period (Part 1)	
Report for: Part 1; Summarize by: dose level (Refer to Section 5.1 for ordering of dose level and omit 1.92 mg/kg if data is not available)
 
An event will be considered a DLT if meets at least one of the criteria defined from Section 4.2.3.1 of the protocol and is considered by the investigator to be clinically relevant and attributed (definitely, probably, or possibly) to the study therapy during the 21 day DLT observation period. Add footnote, "Withdrawn subjects for other reasons other than toxicity, but prior to completion of DLT period were replaced in the study"
	P-SAC [3], F-SAC [4]
Performance Status					
3.0090	All Treated	PS1A	Summary of ECOG Performance Status	
Report for: Part 1, Part 2, and combined Part 1 and Part 2; Summarize by: dose level (Refer to Section 5.1 for ordering of dose level and omit 1.92 mg/kg if data is not available) Total.
	P-SAC [3], F-SAC [4]
3.0091	All Treated	PS3A	Summary of Change in ECOG Performance Status from Baseline	
Report for: Part 1, Part 2, and combined Part 1 and Part 2; Summarize by: dose level (Refer to Section 5.1 for ordering of dose level and omit 1.92 mg/kg if data is not available) Total.
	P-SAC [3], F-SAC [4]

Safety: Tables					
No.	Population	IDSL / Example Shell	Title	Programming Notes	Deliverable [Priority]
Anti-Drug Antibody					
3.0092	All Treated	See programming notes	Summary of Human Anti-GSK2857916 Antibodies (ADA) Over Time	Report for: Part 1, Part 2, and combined Part 1 and Part 2; Summarize by: dose level (Refer to Section 5.1 for ordering of dose level and omit 1.92 mg/kg if data is not available) Total. Refer to mid205678 (primary_01) Table 3.0710 for guidance. For all time points, under the "Subjects with Screening ADA Results", replace "negative conclusive" and "negative inconclusive" with "Negative"; Include titer value summary statistics for confirmed positive; Include the following footnotes: Note: A subject is considered to have a positive ADA result if they have a positive screening assay, a positive confirmation assay and a titer value. A baseline ADA result is the closest ADA sample (i.e. either Screening Visit or Cycle 1 Day 1 Visit) prior to the subject receiving the first dose of GSK2857916. Only confirmed ADA positive samples were tested in the Neutralizing Antibody assay."Note: ADA sample was collected at the time of start of infusion without PK sample." Note: Negative are subjects with all negative results or confirmed negative results.	P-SAC [3], F-SAC [4]

Safety: Tables					
No.	Population	IDSL / Example Shell	Title	Programming Notes	Deliverable [Priority]
3.0093	All Treated	See programming notes	Summary of Anti-GSK2857916 Antibodies (ADA)	
Report for: Part 1, Part 2, and combined Part 1 and Part 2; Summarize by: dose level (Refer to Section 5.1 for ordering of dose level and omit 1.92 mg/kg if data is not available) Total.
 
Refer to mid205678 (primary_01) Table 3.0720 for guidance. For the results relating to negative post-baseline ADA results, combine both sub-categories and classify the results as "negative" and remove total antibody concentration threshold and missing statements;
 
Include the following footnotes:
 
Note: A subject is considered to have a positive ADA result if they have a positive screening assay, a positive confirmation assay and a titer value. A baseline ADA result is the closest ADA sample (i.e. either Screening Visit or Cycle 1 Day 1 Visit) prior to the subject receiving the first dose of GSK2857916. Only confirmed ADA positive samples were tested in the Neutralizing Antibody assay.
 
Note: ADA sample was collected at the time of start of infusion without PK sample.
	P-SAC [3], F-SAC [4]

Safety: Tables					
No.	Population	IDSL / Example Shell	Title	Programming Notes	Deliverable [Priority]
3.0094	All Treated	IMM4	GSK2857916 Immunogenicity Incidence and Summary	Report for: Part 1, Part 2, and combined Part 1 and Part 2; Summarize by: dose level (Refer to Section 5.1 for ordering of dose level and omit 1.92 mg/kg if data is not available) Total. Do not include optional rows, 'Persistent ADA' and 'Transient ADA'.	F-SAC [4]

CONFIDENTIAL

205207

Safety: Tables					
No.	Population	IDSL / Example Shell	Title	Programming Notes	Deliverable [Priority]
COVID-19 Assessments					
3.0095	COVID-19	PAN1A	Summary of COVID-19 Assessments for Subjects with Suspected, Probable or Confirmed COVID-19 Case Diagnosis	Report for: Part 1, Part 2, and combined Part 1 and Part 2; Summarize by: dose level (Refer to Section 5.1 for ordering of dose level and omit 1.92 mg/kg if data is not available) Total; only if greater than 5 participants with COVID-19 infection; If less than 5 participants with COVID-19 infection, produce listing instead; For footnote 1, use 20-Mar-2020 date as per COVID-19 Case Definition for Trials and Event Reporting Guidance	P-SAC [3], F-SAC [4]
3.0096	COVID-19	PAN3A	Summary of COVID-19 Symptoms for Subjects with Suspected, Probable or Confirmed COVID-19 Case Diagnosis	Report for: Part 1, Part 2, and combined Part 1 and Part 2; Summarize by: dose level (Refer to Section 5.1 for ordering of dose level and omit 1.92 mg/kg if data is not available) Total; only if greater than 5 participants with COVID-19 infection; If less than 5 participants with COVID-19 infection, produce listing instead;	P-SAC [3], F-SAC [4]

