8.8.4. Immunogenicity Analyses

For each subject, the results and titers of anti-belantamab mafodotin binding antibodies and neutralizing antibody assay results will be listed for each assessment time point, along with ADC and total antibody concentration. The frequency and percentage of subjects with positive and negative anti-drug antibody and neutralizing antibody assay results will be summarized for each assessment time and overall for each subject by dose cohort.

The number and percentage of subjects with baseline anti-drug antibody results, overall and split by negative and positive samples in each treatment group will be provided. A further summary of subjects with post-baseline anti-drug antibody and neutralizing antibody results, anti-drug antibody negative (overall and for treatment-unaffected only), and treatment-emergent anti-drug antibody results (overall and split by treatment-induced and treatment-boosted) in each treatment group will be presented. Treatment-emergent anti-drug antibody is the sum of treatment-induced anti-drug antibody subjects and treatment-boosted anti-drug antibody positive subjects. Treatment unaffected anti-drug antibody is defined as a subject with an ADA-positive sample at baseline, in which post-baseline sample titer results are less than or equal to a four-fold increase in titer values relative to the baseline titer value (titer \leq 4x baseline titer) or was ADA negative anytime post baseline.

For treatment-induced and treatment-boosted subjects, a summary of all their titer values will be presented. Treatment-induced anti-drug antibody is defined as a subject with at least one post-baseline anti-drug antibody positive sample and an anti-drug antibody negative or missing baseline sample. Treatment-boosted anti-drug antibody is defined as a subject with an anti-drug antibody positive baseline sample in which at least one post-baseline sample titer value is four-fold greater than the baseline titer value (titer $>$ 4x

baseline titer) or if titer result is missing at baseline or missing at all post-baseline assessments.

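### The footnotes to Tables 3.0092 and 3.0093 require a titer for a positive ADA result, but Section 8.8.4 classifies an ADA-positive baseline sample whose titer is missing

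*SAP*

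**What the plan says.** The footnotes to Tables 3.0092 and 3.0093 (SAP Section 16.11.7) carry the same rule. A subject has a positive ADA result "if they have a positive screening assay, a positive confirmation assay and a titer value". The three conditions are joined by *and*.

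Table 3.0092 adds a note on the other category: "Negative are subjects with all negative results or confirmed negative results". Table 3.0093 has no such note. Its programming instruction merges two negative sub-categories without saying what negative means.

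SAP Section 8.8.4 sets out the subject-level categories:

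- "Treatment-boosted anti-drug antibody is defined as a subject with an anti-drug antibody positive baseline sample" in which a later titer exceeds four times baseline, "or if titer result is missing at baseline or missing at all post-baseline assessments".
- "Treatment-induced anti-drug antibody is defined as a subject with at least one post-baseline anti-drug antibody positive sample", together with a negative or missing baseline sample. No titer is mentioned.
- Treatment-emergent ADA is the sum of the induced and boosted subjects.

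Table 3.0094, the immunogenicity incidence table produced at the final analysis only, gives a standard shell reference and no definition of positive. Incidence and titers of ADA are a secondary endpoint in both parts (SAP Section 2.2).

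**The concern.** Section 8.8.4 foresees a baseline sample that is ADA-positive but has no titer, and assigns the subject to a category. The table footnotes say that such a sample is not positive at all. A programmer cannot follow both rules for that subject.

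What is at stake is the count of ADA-positive subjects for a secondary endpoint. Applied literally, the footnote leaves a confirmed positive without a titer out of the positive count, and Table 3.0092 has no defined category to receive it. The endpoint names incidence and titer as two things to report, yet the footnote makes the first depend on the second.

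**Working it through.** The SAP gives no ADA incidence and no count of missing titers, so there is no stated figure to reproduce. The check is to apply each rule to the same sample, and then to show what one subject is worth.

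**Test case: screening positive, confirmation positive, no titer**

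| Place in the SAP | Result |
|---|---|
| Table 3.0092 | Not positive (no titer). Not Negative (neither all negative nor confirmed negative). Unclassified. |
| Table 3.0093 | Not positive. Negative is undefined, so the status is open. |
| Section 8.8.4, sample is the baseline sample | Treatment-boosted, through the missing-baseline-titer branch. |
| Section 8.8.4, sample is post-baseline and baseline is negative or missing | Treatment-induced, unless the footnote's meaning of positive is carried over. |

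**Where the two rules exclude each other**

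1. The boosted definition starts from a positive baseline sample.
2. Under the footnote, a positive sample always has a titer.
3. A positive baseline sample with a missing titer therefore cannot exist, and that branch of Section 8.8.4 could never apply.

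This holds whatever the number of missing titers.

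**Direction**

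The footnote adds a condition, so the positive count in Tables 3.0092 and 3.0093 can only be equal or lower. It is lower only if a confirmed positive lacks a titer.

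The treatment-emergent total behaves differently. Take a subject with an untitered positive baseline and a titered positive sample later:

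- Section 8.8.4 as written: boosted = 1, induced = 0, sum = 1.
- Footnote applied, with the baseline then taken as negative or missing: boosted = 0, induced = 1, sum = 1.

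The total is unchanged for this subject.

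**Size per subject**

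Inputs are the planned numbers in SAP Section 2.3: about 12 in Part 1 and about 28 in Part 2, so 12 + 28 = 40. The change in the proportion for k affected subjects is k/N.

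| N | k = 1 | k = 2 |
|---|---|---|
| 40 (both parts) | 1/40 = 2.5 points | 2/40 = 5.0 points |
| 28 (Part 2) | 1/28 = 3.6 points | 2/28 = 7.1 points |
| 12 (Part 1) | 1/12 = 8.3 points | 2/12 = 16.7 points |

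The value of k is an assumption. With k = 0 the effect is zero.

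**The case against.** The strongest reply is that the conflict may be empty in practice. If every confirmed positive sample is titered, the two rules produce the same tables. ADA is summarised descriptively, with no test or decision rule attached. Listing 1.0064 already has separate columns for screening, confirmation, titer and neutralizing results, so an untitered positive would be visible there. All of this stands, and it limits the size of the point.

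Several stronger readings are tempting, and the SAP does not support them:

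- *ADA incidence is understated.* This needs at least one confirmed positive without a titer, and the plan does not say that any exists. Only *may be understated* is supportable.
- *Such a subject is neither positive nor negative in both tables.* This is explicit for Table 3.0092 only. Moreover, the layouts follow shells from another study that are not shown. The request in Table 3.0092 for titer statistics among confirmed positives might mean that rows are split by assay step, in which case the subject could still appear on a confirmed-positive line.
- *All of Section 8.8.4 contradicts the footnote.* The treatment-induced wording is silent on titers, and silence is compatible with the footnote. The branch for titers missing at every post-baseline assessment can apply to a subject whose baseline is positive and titered. Only the missing-baseline-titer branch conflicts directly.
- *Table 3.0094 will disagree with the other two tables.* The SAP does not say which definition Table 3.0094 uses. Disagreement is possible but not shown.
- *Neutralizing results will appear for subjects not counted as positive.* The footnotes send confirmed ADA-positive samples to that assay, which can be read under the definition given just before.

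One could also align the other way, by removing the missing-baseline-titer branch from Section 8.8.4. That would restore consistency, but would leave a confirmed positive without a titer outside both categories of Table 3.0092.

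**Conclusion.** The point holds in a limited form. The footnotes to Tables 3.0092 and 3.0093 and the missing-baseline-titer branch of Section 8.8.4 cannot both be applied, and Table 3.0092 leaves a confirmed positive without a titer unclassified. The positive count in these tables may be too low if such samples occur.

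The size is unknown. It would be 2.5 percentage points per affected subject overall or 3.6 points in Part 2, assuming that the denominators equal planned enrolment rather than the number of subjects with ADA results. The treatment-emergent total need not change. The matter is worth correcting because the plan itself foresees positives without a titer, the endpoint is secondary in both parts, and the repair is small.

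**What to change.** 1. State one definition of ADA-positive, namely positive on screening and positive on confirmation, in Section 8.8.4, and use it for Tables 3.0092, 3.0093 and 3.0094.
2. Delete the titer condition from the footnotes to Tables 3.0092 and 3.0093.
3. In those tables, show a row for positive subjects with no titer available.
4. Limit titer summary statistics to positives with a titer.

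Listing 1.0064 needs no change. The cost is a footnote edit and one derivation flag, with no new data. The small downside is that reported incidence may be slightly higher.
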